9. STUDY PROCEDURES

a) Provide a detailed description of all study procedures and intervention(s) each subject and/or cohort will experience. Provide a schedule of visits and the procedures that occur at each visit (e.g., tests, questionnaires, surveys, imaging or other interventions.). If the study also involves standard of care, differentiate between research only procedures and standard of care.

Response:

Determine the clinical response of SD and SD/VT symptoms to sodium oxybate using a double-blind, placebo-controlled, randomized, cross-over study design.

The experimental design includes (1) screening for study eligibility; (2) an objective standardized alcohol challenge test for assessment of symptom responsiveness to alcohol, and (3) a double-blind, placebo-controlled, randomized, crossover study of sodium oxybate. The **primary outcome** will be to determine the response of SD and VT symptoms to sodium oxybate 40 min after administration, compared to placebo. We will recruit the following groups of patients:

- (1) ETOH+ SD and SD/VT who report positive effects of alcohol on their voice symptoms;
- (2) ETOH- SD and SD/VT who report no effects of alcohol on their voice symptoms, and Although our prior studies have shown that sodium oxybate has similar effects in both SD and SD/VT patients as well as in ADSD and ABSD, the inclusion of these patients will allow to capture the entire SD populations and to cross-validate our findings. On the other hand, the inclusion of negative controls with ETOH- SD and ETOH- SD/VT will allow for enhanced explanations of our findings and delineation of the primary factors contributing to the pathophysiology of SD and VT with respect to treatment outcome.

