Randomization and Allocation. Following the alcohol challenge, patients will be randomized for the double-blind, placebo-controlled, cross-over study. The randomization will be performed by the MEEI Research Pharmacy and will be blinded for the investigators and patients. The study will be conducted under the existing Investigational New Drug (IND) application granted to the PI by the US Food and Drug Administration (FDA) for the use of sodium oxybate in SD and SD/VT patients (#117,954). Patients will be allocated 1:1 to a treatment sequence #1 of sodium oxybate/placebo or sequence #2 of placebo/sodium oxybate. Jazz Pharmaceuticals, Inc., will provide sodium oxybate and the matching placebo for research purposes, which will be sent directly to the MEEI Research Pharmacy. The placebo will be a clear solution with salty taste that matches the appearance and taste of the drug. Sodium oxybate (1.5 g = 3 ml) of oral solution diluted in 47 ml of water) and the placebo (50 ml) will be formulated in sequentially numbered containers by the research pharmacy in the morning of administration. Both patients and investigators will be blinded until all outcome data are processed and the database is locked at the end of the study. EPIC will be used for study drug dispensing to ensure accurate and complete documentation.

Study drug will be administered by a licensed physician associated with this protocol.

As stated above under the *General Study Procedures* section, all patients will be assessed for their vital signs, MoCA, C-SSRS, side effects, and sleepiness immediately before and 45, 180, 300 min after drug/placebo intake. As a primary outcome measure, voice and speech recordings will be performed at the same time points. Data will be de-identified, randomized, and blindly rated for symptom severity, as described above. Our prior studies have shown that the effects of sodium oxybate (1-1.5 g) in ETOH+ movement disorders are obvious 30-45 min following drug intake and last approximately 3.5-4 hours (Frucht et al., 2005a; Frucht et al., 2005b; Arpesella et al., 2009; Simonyan and Frucht, 2013; Rumbach et al., 2016).

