10. STUDY OUTCOMES

a) **Primary Outcome Measure(s)** - describe how you will measure the primary and other outcomes of the study (e.g., blood pressure change, changes in visual acuity using a specific test, pain scales, responses on a questionnaire, etc.). Upload copies of your data collection tools and/or a list of all variables/data points you will collect.

Note: Primary outcome measures may be measured in various ways such as:

- binary (e.g. improvement in symptoms vs. no improvement in symptoms)
- continuous (e.g. weight kg, blood loss mL)
- ordinal (e.g. pain mild, moderate, severe)
- time to event (e.g. survival)
- counts (e.g. number of infections, number of events occurring)

Response: Primary outcome measures will include clinical improvement of voice symptoms.

b) Describe any secondary or other outcomes (exploratory): N/A

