12. STATISTICAL METHODS

Describe the planned statistical methods including specific tests (e.g., parametric and non-parametric tests, estimation of incidence and prevalence rates, odds ratios, survival/failure analyses, intent to treat analyses). Provide the power calculations used to estimate the proposed sample size. If needed, please consult a biostatistician. (Note: Biostatistical consults are available through Harvard Catalyst.)

Response:

Audio recordings will be de-identified, randomized and blindly rated to count the voice breaks as well as to quantify harshness, breathiness, tremor, and hoarseness using a visual analog scale with three gradation indicators along a 100-mm line (normal, modulates voice, offsets voice), with distance in mm denoting the degree of deviancy from normal, as described earlier (Kirke et al., 2016). Alcohol Challenge Test. All individual measures before and after alcohol intake will be compared using the equation ((Baseline-Alcohol Challenge)/Baseline) \times 100%. To account for potential subjective bias and ensure reliable alcohol effects on voice symptoms, we will consider patients with \geq 10% change of their symptoms from baseline as responsive to alcohol (ETOH+) (Haubenberger et al., 2013; Voller et al., 2014). As a secondary outcome, we will compute Pearson's correlations between symptom scores and brAC measures to examine the baseline and each time point in respect to alcohol content at a corrected p \leq 0.05.

Analysis. The primary outcome within each group will be examined using a linear mixed effect model with treatment (sodium oxybate and placebo) and treatment visits as interacting fixed effects and a per subject random effect at overall $p \le 0.01$ to correct for multiple comparisons. If the interaction between the fixed effects is significant, the difference between treatments will be tested using linear contrasts of least-squares means for the fitted model at $p \le 0.05$ adjusted for multiple comparisons. As a secondary analysis, benefit ratio will be calculated as (sodium oxybate effect – placebo effect) and analyzed using a Friedman test at $p \le 0.01$.

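### Cheap improvement: the pre-dose voice recording at each treatment visit has no stated place in the primary model; adding it as a covariate may buy precision

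*Combined protocol and SAP*

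**What the plan says.** Section 9 (Randomization and Allocation) sets the assessments at each treatment visit "immediately before and 45, 180, 300 min after drug/placebo intake", and adds: "As a primary outcome measure, voice and speech recordings will be performed at the same time points". The recordings are rated blind, so a rated pre-dose score exists for both treatment visits.

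Section 12 (Analysis) specifies a linear mixed model with "treatment (sodium oxybate and placebo) and treatment visits as interacting fixed effects and a per subject random effect". No pre-dose term is named.

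The response variable is not defined. Section 9 gives the primary outcome as the "response of SD and VT symptoms to sodium oxybate 40 min after administration, compared to placebo". Section 10 says only: "Primary outcome measures will include clinical improvement of voice symptoms". The one explicit baseline formula, percent change from baseline, belongs to the alcohol challenge: "All individual measures before and after alcohol intake will be compared using the equation". The secondary benefit ratio subtracts a placebo effect from an oxybate effect without defining either.

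**The concern.** A per-subject random effect removes stable differences between patients. It does not remove the difference between one patient's severity on the oxybate day and on the placebo day. If that difference is material, it stays in the oxybate-placebo contrast as noise, although the pre-dose recordings measure it directly.

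Two things are at stake. The first is precision, in cohorts of about 22 analysed patients tested at 0.01. The second is that the role of the pre-dose score is left open. Ignoring it, subtracting it and adjusting for it can give quite different power, and the plan does not choose among them.

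**Working it through.** **1. The plan's own figure.** Section 5 states 22 patients for 80% power at 0.0125 by a binomial test, from a response rate of 37/45 = 82.2%. The null rate and sidedness are not given. With an assumed null of 0.5 and a one-sided exact test, 22 is the smallest sample reaching 80%: success at 17 or more of 22, actual alpha 0.0085, power 81.6%. The figure reproduces. It concerns a response rate, so how the mixed model handles the pre-dose score does not change it.

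**2. Quantity that drives the gain.** For each patient take the oxybate-minus-placebo difference in post-dose scores and the same difference in pre-dose scores. Let rho be the correlation between these two differences. If w is the pre/post correlation within a visit and b the correlation between visits, then

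rho = (w − b)/(1 − b).

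For example, w = 0.8 and b = 0.6 give 0.2/0.4 = 0.5. If visits add nothing beyond the stable patient level (w = b), rho = 0.

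**3. Variance of the treatment contrast, relative to ignoring the pre-dose score.**
- Covariate: (1 − rho²) × [1 + 1/(n − 4)]. The bracket is the price of estimating one more slope; at n = 22 it is 1 + 1/18 = 1.056.
- Raw change from pre-dose: 2(1 − rho).

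**4. Power.** Assumptions, none of them in the documents: standardised difference d = 0.75 (mean difference divided by the SD of the within-patient difference), two-sided testing, and the values of rho. Alpha 0.01 is from section 12 and n = 22 from section 5. Unadjusted, the noncentrality is 0.75 × √22 = 3.52 on 20 degrees of freedom, giving power of about 74%. With the covariate, noncentrality is 3.52/√(variance ratio) on 19 degrees of freedom.

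| rho | Variance ratio, covariate | Power, covariate | Variance ratio, raw change | Power, raw change |
|---|---|---|---|---|
| 0 | 1.06 | 71% | 2.0 | 39% |
| 0.2 | 1.01 | 73% | 1.6 | 49% |
| 0.3 | 0.96 | 76–77% | 1.4 | 56% |
| 0.5 | 0.79 | 85% | 1.0 | 74% |
| 0.7 | 0.54 | 96% | 0.6 | 94% |

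Simulation of 20,000 trials per setting agrees within simulation error. The covariate breaks even at rho of about 0.2 to 0.25. Raw change breaks even at 0.5, and is no better than the covariate at any rho in the table.

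**5. Sensitivity.** If the effect is set so that unadjusted power is 80% at n = 22, the covariate gives 77%, 79%, 81%, 89% and 98% at the same values of rho, which is the same pattern. With 35 completers, the recruitment ceiling per cohort, and d = 0.75, unadjusted power is already about 95%, and rho = 0.5 adds 3 to 4 points.

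**The case against.** **A reader might infer that the pre-dose recording goes unused.** The documents do not establish this. Response and clinical improvement could both mean change from pre-dose. The term treatment visits could also mean the repeated recordings rather than the two days. The rule that a significant interaction opens the treatment contrasts fits a treatment-by-time model, in which the pre-dose rows would be part of the data. This part of the objection stands: what can be said is that no pre-dose term is named and the response is undefined. It does not remove the point. A baseline-referenced interaction in such a model is in effect a raw change, and covariate adjustment does at least as well at every rho tried.

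**A reader might infer bias.** Order is randomised 1:1 to the two sequences, so omitting the covariate does not bias the comparison.

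**A reader might call the precision free, or take day-to-day variation as given.** Neither is supported. Below rho of about 0.2 the covariate costs a little power. The documents give no within-patient SD, correlation or interval between visits. They also take steps that limit variation: patients must be fully symptomatic after botulinum toxin before entry, those on CNS-acting drugs are excluded, and alcohol and caffeine are withheld for 48 hours before visits. If treatment visits means the two days, that term also removes average drift between them. Patient-specific differences can still remain, and no re-check of symptom status at each treatment visit is stated.

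**A reader might infer that the sample size is wrong on this account.** It is not: the 22 comes from a binomial calculation.

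**Conclusion.** The point holds as a cheap improvement. A rated pre-dose score is collected at both treatment visits, and the plan neither names a term for it nor defines the response variable that would settle its role. The consequence is a possible loss of precision, with no threat to validity.

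The size depends on an unknown rho. At n = 22, with d = 0.75 assumed, the effect on power ranges from a loss of about 3 points at rho = 0 to gains of about 10 points at 0.5 and 22 at 0.7. If all 35 patients in a cohort complete, little is left to gain. The downside is small and bounded, while the upside is substantial if severity differs between a patient's two visits.

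**What to change.** Before database lock:

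- Define the primary response as the post-dose score at the primary time point, and say what treatment visits denotes. Section 9 gives 40 minutes for the outcome but 45 minutes for the recording; these need reconciling.
- Add the same-visit pre-dose score to the primary model as two terms: the patient's mean over the two visits, and each visit's deviation from that mean. Only the deviation affects the within-patient treatment contrast.
- State that raw change from pre-dose will not be used in place of this adjustment.

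No new data are needed. The cost is two model terms, about one within-patient degree of freedom, and about 3 points of power at n = 22 if rho is in fact 0 (with d = 0.75). The stated sample size stays as it is.

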10. STUDY OUTCOMES

a) **Primary Outcome Measure(s)** - describe how you will measure the primary and other outcomes of the study (e.g., blood pressure change, changes in visual acuity using a specific test, pain scales, responses on a questionnaire, etc.). Upload copies of your data collection tools and/or a list of all variables/data points you will collect.

Note: Primary outcome measures may be measured in various ways such as:

- binary (e.g. improvement in symptoms vs. no improvement in symptoms)
- continuous (e.g. weight kg, blood loss mL)
- ordinal (e.g. pain mild, moderate, severe)
- time to event (e.g. survival)
- counts (e.g. number of infections, number of events occurring)

Response: Primary outcome measures will include clinical improvement of voice symptoms.

b) Describe any secondary or other outcomes (exploratory): N/A

11. HYPOTHESES

Hypotheses are more specific than specific aims and are tested using predetermined statistical methods and form the basis for statistical power calculations. The primary hypothesis is a statement of the effect of the research intervention/interaction on the primary outcome measure. Hypotheses are generally stated as the null and alternative hypotheses (H0, Ha) as they have their basis in inferential statistics. Rejecting the null hypothesis with a specific level of probability indicates that there is a relationship between the variables being studied. State the alternative hypothesis which you expect your data to support.

Examples of null and alternative hypotheses

- H0: Chronic sinusitis prevalence rates are not different among children from low and high socioeconomic groups
- Ha: Chronic sinusitis prevalence rates are different among children from low and high socioeconomic groups.
- a) Describe the primary hypothesis:

Response: H0: Similar to alcohol and placebo, sodium oxybate is not effective in reducing LD symptoms in EtOH+ patients but not EtOH- patients.

Ha: Similar to alcohol and in contrast to placebo, sodium oxybate is effective in reducing LD symptoms in EtOH+ patients but not EtOH- patients.

b) Describe any secondary hypotheses.

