Significance of the Expected Research Contribution. Our contribution here entails the detailed understanding of the primary contributing factors that underlie the clinical benefits of sodium oxybate in ETOH+ SD and SD/VT patients. Our rigorous experimental approach will include symptom evaluation based on the objective alcohol challenge test and double-blind, placebo-control, randomized, cross-over study design to identify the primary determinants of sodium oxybate response in ETOH+ SD and SD/VT patients. The expected outcome of these studies will allow for translations from bedside to bench and bedside again, maximizing integration between clinical and basic aspects of this research program. Collectively, the proposed studies have strong scientific premise because they will allow for delineation of the mechanistic aspects of sodium oxybate's effects on SD and VT pathophysiology. As such, successful completion of the proposed studies will establish a muchneeded scientific rationale for the future large clinical trials and the ultimate use of sodium oxybate as a therapeutic option for treatment of SD and VT. This will be especially important for those patients who have suboptimal response to botulinum toxin treatment or forgo it due to personal or medical issues. Thus, this contribution will be significant because it is expected to have a broad translational impact on improving the clinical management of patients with SD and VT. It is further expected that our findings will be equally applicable to the treatment of other forms of ETOH+ dystonia and dystonic tremor. Taken together, the proposed rigorous experimental approach to identify an effective oral medication for SD and SD/VT based on disorder pathophysiology will represent a significant departure from the existing trial-and-error attempts to treat these disorders. It will represent a novel therapeutic approach directed to the treatment of the disorder per se rather than temporary management of voice symptoms as with the current use of botulinum toxin.

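### The alcohol clause in H0 and Ha is settled by how EtOH+ is defined, and the claim of benefit in EtOH+ but not EtOH− patients has no test

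*Combined protocol and SAP*

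**What the plan says.** Section 11 a) puts alcohol into both primary hypotheses. The null reads "H0: Similar to alcohol and placebo, sodium oxybate is not effective in reducing LD symptoms in EtOH+ patients but not EtOH- patients". The alternative reads "Ha: Similar to alcohol and in contrast to placebo, sodium oxybate is effective in reducing LD symptoms in EtOH+ patients but not EtOH- patients".

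The label EtOH+ is defined in two ways. Section 12 (Alcohol Challenge Test) counts a patient as responsive on at least a "10% change of their symptoms from baseline as responsive to alcohol (ETOH"+), using an equation in which improvement is positive. Section 9 a) forms the recruitment groups by self-report: "ETOH+ SD and SD/VT who report positive effects of alcohol on their voice symptoms".

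The challenge has its own visit and comes first: "Following the alcohol challenge, patients will be randomized for the double-blind, placebo-controlled, cross-over study". Section 9 describes no placebo for alcohol. It does say that recordings are de-identified, put in random order and rated blind.

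The primary outcome in section 9 is oxybate against placebo. The section 12 model has those two treatments, crossed with visit, and is fitted within each group. Section 4 nevertheless sets the EtOH+ response against the EtOH− response, and section 3 promises "to identify the primary determinants of sodium oxybate response in ETOH+ SD and SD/VT patients". Section 11 b) states no secondary hypothesis.

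**The concern.** A primary hypothesis should contain only statements that the data can contradict. Under the section 12 rule, nobody in the EtOH+ group can fail to have responded to alcohol at the challenge, because that response is what put them there. The alcohol part of H0 therefore cannot be true in that group, and the alcohol part of Ha cannot be false.

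Two things are at stake. First, a positive result reported in the words of Ha would carry an alcohol claim that has no placebo control and no possible negative outcome. Section 3 says the trial is needed because a placebo effect could not be excluded in open-label work, so this matters here. Second, the part of Ha that could be informative, that oxybate benefit depends on alcohol responsiveness, is left to a comparison of separate within-group results.

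**Working it through.** **1. Each clause against the planned analysis.**
- Oxybate differs from placebo in EtOH+: tested by the mixed model within that group.
- Alcohol works in EtOH+: no model term, and the answer is fixed by the classification rule.
- Oxybate is like alcohol: no test compares the two, and alcohol is not a randomised treatment.
- Benefit in EtOH+ but not in EtOH−: two within-group fits, with no group term and no alcohol-response term.
- The section 12 benefit ratio (oxybate effect minus placebo effect) goes to a Friedman test. That ranks repeated measures within patients and cannot compare independent groups.

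**2. The plan's sample size.** Section 5 gives 22 patients for 80% power at 0.0125, from 37/45 = 82.2%. An exact binomial test with p0 = 0.50, one-sided (both are assumptions, as neither is stated), rejects at 17 or more of 22 and has power 81.6%. No smaller n reaches 80%. Alcohol does not enter this calculation.

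**3. Does selection on the alcohol visit disturb the oxybate test?** Simulation: no true effect of alcohol or oxybate; 22 patients selected at 10% or more on the alcohol visit; a paired t-test at 0.0125 standing in for the mixed model; 2,000 runs for each assumed SD of percent change.
- Alcohol clause tested on the same challenge data: rejected in 100% of runs at SD 10, 20 and 30.
- Oxybate minus placebo: rejected in 1.1%, 1.6% and 1.6% of runs. The simulation standard error is √(0.0125 × 0.9875 / 2000) = 0.25 percentage points, so these agree with 1.25%.
- With a stable non-specific responder trait (assumed SD 15) carried into both treatment visits, and noise SD 10 or 20: 1.0% and 1.6%. Both arms improve, by about 15% and 9%, and the difference between them is unaffected.

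**4. How much apparent alcohol benefit selection alone can create.** Illustration only. Assume no true alcohol effect, one measure at one time, and a normal percent change with mean 0. Share labelled EtOH+: P = 1 − Φ(10/SD). Mean apparent benefit among them: SD × φ(10/SD) / P.
- SD 10: P = 0.159; 10 × 0.2420 / 0.1587 = 15.3%.
- SD 15: P = 0.252; 15 × 0.3194 / 0.2525 = 19.0%.
- SD 20: P = 0.309; 20 × 0.3521 / 0.3085 = 22.8%.

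Section 12 does not name the qualifying measure or time. If any of the five post-dose times may qualify (assumed correlation 0.5), the shares become 41%, 57% and 65%.

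**5. What the missing between-group test costs.** Suppose oxybate has the same true effect in EtOH+ and EtOH− patients, and each within-group test has the planned 80% power. The probability of significance in EtOH+ and none in EtOH− is 0.80 × (1 − 0.80) = 0.16, about one trial in six. This treats the groups as independent and applies the section 5 power to the section 12 test.

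**6. What the added regression would lose to noise.** The slope shrinks by the factor true variance / (true variance + noise variance). With an assumed true between-patient SD of 15 points, noise SD 10 gives 225/325 = 0.69, and noise SD 20 gives 225/625 = 0.36. The shrinkage is toward zero. The alcohol and treatment scores come from different visits, so selection noise does not create a slope.

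**The case against.** The strongest reply is that alcohol enters no primary test, so the clause is loose wording around a sound randomised comparison. That stands, and it limits the point. A reader might infer that the primary null is false by definition, or that the trial is bound to succeed. The documents do not support that: the null that is tested is oxybate against placebo, and step 3 shows that it keeps its level. Nor is oxybate judged against an inflated alcohol benchmark, since the only comparator in sections 9 and 12 is placebo.

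Other limits also stand:
- Being like alcohol can be read as a pattern, benefit in EtOH+ and none in EtOH−. Oxybate can fail that pattern in either group, so the claim is not wholly circular. But this reading needs the between-group test that the plan lacks.
- It would be wrong to say that the alcohol data serve only as a cut-off. Section 12 also correlates symptom scores with breath alcohol. That concerns alcohol exposure and says nothing about oxybate response.
- It is tempting to call the challenge unblinded. Patients probably know that they have taken alcohol, since no placebo is described, but the ratings are blind.
- The question of determinants is not ignored. EtOH− patients are enrolled for that purpose and blood is taken for genetic analysis. What is missing is a formal test.
- Under the section 9 self-report grouping alone, the alcohol clause would not be settled by definition. That calls for the two definitions to be reconciled.
- Baseline and post-alcohol recordings belong to one visit, so day-to-day variation is not the noise in step 4, and repeated pre-alcohol recordings could steady the baseline.

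**Conclusion.** The point holds in limited form. Under the section 12 rule, the alcohol clause of H0 and Ha cannot be tested in EtOH+ patients, and no planned analysis examines likeness to alcohol. Sample size, type I error and the oxybate-versus-placebo estimate are unaffected.

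The more useful finding is that benefit in EtOH+ but not in EtOH− patients is part of the primary hypothesis and has no supporting test. A significant result in one group beside a non-significant one in the other does not show a difference; the 0.16 in step 5 gives the scale, on the assumptions stated there. H0 as worded is also not the complement of Ha.

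The 16% to 31% false-labelling figures are illustrative. They assume no true alcohol effect, which is the extreme case, and SDs that the documents do not give. The change is worth making because it corrects the primary claim at little cost.

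**What to change.** - **Hypotheses (section 11).** Remove the comparison with alcohol from both lines. State H0 for EtOH+ patients as a mean oxybate-minus-placebo difference of zero, and Ha as a non-zero difference.
- **EtOH− part.** Keep it as a separate hypothesis, with the null that the oxybate-minus-placebo difference does not vary with alcohol response.
- **Secondary analysis (section 12).** Pre-specify one analysis in all randomised patients, whatever their label: regress each patient's oxybate-minus-placebo difference on the continuous alcohol-challenge change, with treatment sequence as a covariate. A treatment-by-alcohol-response interaction in the mixed model would serve equally.
- **Definitions.** Name the voice score used on both sides of that analysis and the alcohol time point; sections 10 and 12 leave these open. Reconcile the self-report grouping in section 9 with the 10% rule in section 12, and say which one defines the analysis groups.
- **Reporting.** Present alcohol-visit change in EtOH+ patients as the classifier and not as evidence of efficacy.

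The cost is a rewrite of section 11 a), the definitions above, and one extra analysis. No new data are needed: the alcohol response is already collected, and section 12 already derives the oxybate-minus-placebo effect. The sponsor gives up the alcohol wording in the primary claim. The plan should state that noise in the alcohol score pulls the slope toward zero, so a flat slope would not prove that alcohol response is irrelevant.
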